Upon entry in the clinical trial, the master study database (REDCap, described later in Section 16) will randomly allocated patients to one of the study arms (1:1) within site (1:1) using a computer generated random sequence. This will provide an allocation sequence for each site. Once a patient is enrolled and a database file in REDCap is initiated for that patient, he/she will be assigned electronically to one of the study arms.

Patient will be blind to the intervention but surgeon blinding will not be feasible due to the nature of the intervention. The study will involve a considerable number of surgeons in each site, which should compensate any potential bias of some of them in favor or against either approach.

e. Flow chart

Multi-center Study Protocol: Efficacy of Near Infrared Incisionless Fluorescent Cholangiography (NIFC) during Laparoscopic Cholecystectomy

[figure not shown]
Figure 1 shows the flow chart for the study, a multi-centered randomized controlled trial (RCT) 1:1 with two arms:

1. Control: WLI

A laparoscopic cholecystectomy will be performed using Xenon white light imaging (WLI) only.

2. Experimental: NIFC

A laparoscopic cholecystectomy will be performed using both white light imaging and near infrared light imaging with indocyanine green (ICG) intravenous dye.

9. Data collection and procedures

Data will be collected before, during and at the end of surgery; and one week after surgery.

a. Pre-Op data collection

i. Patient data

- Age
- Gender
- Weight
- Height
- BMI

ii. Patient clinical characteristics

- Liver disease
- Lithiasis
- Surgical status: elective/urgent/emergent

b. Intra-Op data collection

i. For NIFC arm only

- Time of ICC administration
- Was there any Adverse Reaction? If so, what happened and how was the patient treated?

ii. For both arms: PRIOR to dissection

- Categorize initial visualization
 - Amount of fat
 - Amount of inflammation
 - Presence of adhesions / scar tissue
- Remove the fat from the Calot's triangle area, retract the gallbladder and Hartmann's pouch
- Surgeon/Observer documents which extra-hepatic biliary structures are identified without doubt
- Start Dissection. Document the time hilar dissection was begun (baseline time)

iii. For both arms: AFTER dissection

- Surgeon/Observer documents which extra-hepatic biliary structures are identified without doubt
- Time to Clip: Document the time the Cystic Duct was clipped
- Volume of Bleeding
- Incidence of Bile Leakage

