3. After removing the fat from the gallbladder area, lifting the gallbladder over the liver, and grabbing the Hartman's pouch to visualize the Calot's triangle, but PRIOR TO DISSECTION, the Researcher will use NIFC to determine what extra-hepatic biliary structures can be specifically identified. This involves toggling the light source back and forth between STD mode (WLI) and ICG mode (NIFC). Of note: because one of the goals of the Study is to evaluate NIFC as a teaching tool, residents and juniors should record what structures they were able to identify by themselves before any intervention of the attendant surgeon.
4. Then, AFTER DISSECTION, a similar assessment of what extra-hepatic biliary structures can be specifically identified using NIFC will be performed.
5. Anatomic anomalies of the biliary system will be documented on the case form and if an anatomic variation is found, a snap shot photo will be taken in addition to the video.
6. Immediately before clipping or proceeding with open surgery, the total time from Step 1 will be recorded, known herein as the "Time to Clip";
7. Before leaving the operation room, all participant surgeons and observers will complete the Intra-Operative Case Report Form (Appendices D and E, respectively).

d. Post-Operative Case Report Form

During the standard follow-up exam, typically 7-10 day post-op, the Researcher will complete the Post-Operative Case Report Form (Appendix F).

e. Bile Duct Injury Form (if needed)

If the procedure results in a bile duct injury, the operating surgeon will complete the ancillary Bile Duct Injury Form (Appendix G).

13. Statistical Plan

a. Sample size

We estimate that the six participant centers will be able to enroll a minimum of 1000 patients in a 12 months period. Table XX shows the minimum effect size (increase in the rate of detection) that we will be able to detect with a 90% power or more, 5% level of significance, one-side test, when the detection rate in the control group are the ones indicated in the first column.

Structure	Before dissection		After dissection	
	DR control group	DR increase (effect size)	DR control group	DR increase (effect size)
Cystic	50%	10%	100%	--
Right Hepatic Duct	40%	10%	80%	7%
Common Hepatic Duct	46%	10%	70%	8%
Common Bile Duct	46%	10%	96%	3%
Cystic-CBD junction	29%	9%	60%	9%
Cystic-Gallbladder junction	60%	9%	70%	8%
Accessory Ducts	1%	3%	2%	4%

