Regarding the main secondary outcome, incidence of injuries, the power to detect a drop from 8/1000 in the control arm to 2/1000 in the intervention arm, with a sample size of 500 patients per arm is 15%. Regretfully, with an achievable sample size as the one proposed above, the study will not have enough power to detect a drop in the incidence as important as the one considered.

b. Data Analysis

In general, descriptive statistics including frequencies and means will be used to characterize patient's baseline characteristics in both study arms. Analyses are designed to test the following hypotheses based on the primary objectives: Compared to those in the control arm, surgeons using NIFC will be able to identify a) more frequently the gallbladder cystic union (both before dissection and before clipping); b) a larger number of hepato-biliary structures and; c) more frequently some of the five hepato-biliary structures. We will test the first hypothesis using the chi-square test, the second one using non-parametric test (e.g. Kruskal-Wallis) and the third one using generalized mixed or hierarchical models to account for the clustering induced by the patient.

Multi-center Study Protocol: Efficacy of Near Infrared Incisionless Fluorescent Cholangiography (NIFC) during Laparoscopic Cholecystectomy

Regression models (logistic or generalized mixed models) will be fitted including covariates to evaluate if the effect of NIFC on the primary outcomes is modified by the patient's or surgeon's characteristics and site.

Regarding secondary outcomes we will use the Fisher's exact test or Chi square test (as needed) to compare proportion of patients with bile duct injury, open surgery or bleeding. Time to clipping and time to end of surgery will be compared between arms using the Kruskal-Wallis' test. Regression models will be used when possible -we expect very low incidence of injuries and open surgeries- to evaluate patient's and surgeon's effect modification.

Finally, for those outcomes specific for the NIFC group we will use logistic or generalized linear models to assess whether the reported helpfulness of the NIR light or the reflux maneuver is associated to patient's characteristics or surgeon's experience.

All statistical analysis will be conducted in R software.

14. Anticipated Problems and Solutions

a. Lower than expected Enrollment

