3. AFTER-DISSECTION

A. Document visualization of extra-hepatic biliary anatomy:

For both arms, scope the Calot's triangle area using STD (white-light) mode. If in the NIFC arm, toggle between STD and ICG modes on light source as needed. Check the appropriate boxes below based on what is visible:

	Yes	Maybe	No
Cystic Duct			
Right Hepatic Duct			
Common Hepatic Duct			
Common Bile Duct (CBD)			
Cystic-CBD junction			
Cystic-Gallbladder junction			
Accessory Ducts			

B. For NIFC Arm Only: "Reflux Maneuver" Attempted? Yes No

Repeat the Reflux Maneuver. Check the appropriate boxes based on what is visible:

	Yes	Maybe	No
Cystic Duct			
Cystic-CBD junction			
Cystic-Gallbladder junction			

4. Time to Clip: Time the Cystic Duct was clipped: _____ AM / PM

5. Volume of Bleeding: _____ mL in the bucket/bag or from anesthesia chart at the conclusion of the procedure

6. Bile Leakage: No Yes If yes, Liver bed Other: _____ Did NIFC help identify leak? Yes No

7. Anatomic Anomalies: No Yes If yes, describe: _____

If yes, do you feel NIFC helped you identify this anomaly? Yes No N/A (WLI arm)

8. Was IOC performed? Yes No

9. Were CBD Stones present? Yes No Not Checked

10. Was the procedure converted to Open? Yes No

If yes, explain why: _____

11. Was there a Bile Duct Injury (BDI) during the surgery? Yes No

If yes, complete the BDI Form as described in the Study Protocol.

12. SURGEON FEEDBACK after NIFC:

Did you feel NIFC made your procedure SAFER? Yes No

Were you more CONFIDENT using NIFC vs WLI alone? Yes No

Would you PREFER to use NIFC again vs WLI alone? Yes No

e. Intra-Op Case Report Form – Observer

Near Infrared Incisionless Fluorescent Cholangiography (NIFC)

INTRA-OPERATIVE CASE REPORT FORM - OBSERVER

INSTITUTION: _____

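### The NIFC-only test of helpfulness against surgeon's experience has no surgeon term, so its standard errors are too small whenever surgeons differ in their opinion of the device

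*Combined protocol and SAP*

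**What the plan says.** The last analysis described in section 13.b covers outcomes specific to the NIFC arm: "we will use logistic or generalized linear models to assess whether the reported helpfulness of the NIR light" varies with features of the patient or the operator. Ratings of the reflux maneuver are handled in the same way. The predictors come at the end of that sentence, where the question is whether helpfulness "is associated to patient's characteristics or surgeon's experience".

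The ratings are collected in item 12 of the surgeon's intra-operative form (Appendix d). It asks, Yes or No, "Did you feel NIFC made your procedure SAFER", and then about confidence and about preference for using NIFC again. A form is completed for each operation. It also records the surgeon's name, title, years in practice and approximate number of these procedures performed. Section 6 lists expertise as resident or attendant.

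Mixed models appear twice elsewhere in 13.b. For the third primary hypothesis the plan uses "generalized mixed or hierarchical models to account for the clustering induced by the patient". For effect modification, "Regression models (logistic or generalized mixed models) will be fitted including covariates". Clustering by surgeon is not mentioned for any model. Section 8.d says "The study will involve a considerable number of surgeons in each site", but offers this as protection against bias between arms and gives no count.

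**The concern.** An ordinary logistic model treats every rating as an independent observation. Here the ratings are repeated opinions from a limited set of people, and the predictor is a property of the person. For such a predictor the information grows with the number of surgeons rather than the number of forms. If some surgeons are enthusiasts and others sceptics for reasons unrelated to experience, the model counts each opinion many times and can report an experience effect that is not there.

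Section 8.d itself expects some surgeons to lean for or against an approach. In an arm comparison within site, such leanings may tend to balance. In this analysis the leaning is the outcome. A statement that NIFC is more helpful to junior surgeons could then rest on a handful of individuals and carry an interval that is too narrow.

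**Working it through.** **Inputs from the documents.** 500 patients per arm (13.a); 1:1 allocation within site (8.d); model and predictor as quoted (13.b). Section 13.a counts six centers while 8.b lists nine sites.

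**Inputs assumed, because the documents do not give them.**
- One rating per NIFC case, so about 500 ratings. Section 12.c has all participating surgeons complete forms, so there could be more.
- 27 to 90 surgeons, that is 3 × 9 to 10 × 9, or 500/27 ≈ 18.5 down to 500/90 ≈ 5.6 cases each.
- A two-sided 5% test. The plan's "5% level of significance, one-side test" belongs to the detection-rate sample size only.
- The within-surgeon correlation and the Yes rate, both varied below.

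**The plan's own figure.** No power or error rate is stated for this analysis. The nearest design figure is the detection-rate table, described as the "minimum effect size (increase in the rate of detection) that we will be able to detect with a 90% power or more". Take the right hepatic duct before dissection, 40% against 50%, with 500 per arm:
- SE under the null = √(2 × 0.45 × 0.55/500) = 0.0315
- SE under the alternative = √((0.24 + 0.25)/500) = 0.0313
- power = Φ((0.10 − 1.645 × 0.0315)/0.0313) = 93.8%

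The 13 cells that state an increase give 89.3% to 94.4%, so the table reproduces. It has no bearing on the helpfulness model.

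**Step 1: design effect.** For a predictor constant within surgeon, with *m* cases each and correlation ICC on the Yes/No scale, DE = 1 + (*m* − 1) × ICC. The true size of the nominal 5% Wald test is 2 × [1 − Φ(1.96/√DE)]. Example: *m* = 10 and ICC = 0.10 give DE = 1.9, 1.96/√1.9 = 1.42, size 15.5%.

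| Cases per surgeon | ICC 0.02 | 0.05 | 0.10 | 0.20 | 0.30 |
|---|---|---|---|---|---|
| 5 | 5.9% | 7.4% | 9.8% | 14.4% | 18.6% |
| 10 | 7.1% | 10.4% | 15.5% | 24.1% | 30.8% |
| 20 | 9.5% | 16.0% | 25.0% | 37.1% | 44.9% |

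The size doubles to 10% once (*m* − 1) × ICC reaches about 0.42, and triples to 15% at about 0.85.

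**Step 2: simulation with uneven caseloads.** 500 ratings were spread unevenly over the surgeons. 40% of surgeons were labelled resident, there was no true experience effect, and a surgeon intercept was added on the logit scale. Latent ICC = SD²/(SD² + π²/3), so SD 0.25, 0.5, 0.9 and 1.2 give 0.02, 0.07, 0.20 and 0.30. False-positive rates of the ordinary logistic test:
- 70–85% Yes, ICC 0.07–0.30: about 13–40% with 27 surgeons, 10–33% with 45, 8–25% with 72, 7–21% with 90.
- 95% Yes, same ICC range: about 5–21%.
- 98% Yes: at or below about 7%.
- ICC about 0.02: about 5–10%.
- No surgeon variation, 70–85% Yes: 4–5%, so the clustering is the cause.

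The inflation fades near the ceiling because the same logit-scale spread then leaves little room for surgeons' Yes rates to differ.

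**Step 3: does clustering by surgeon repair it?** With 25 to 100 surgeons, 80% Yes and a Yes/No-scale ICC of 0.05–0.20, the ordinary model gave 7.6–36.9%. Cluster-robust variance with a *t* reference on (surgeons − 2) degrees of freedom gave 3.5–7.5%. A surgeon-level *t* test gave 3.4–6.1%. Separately, on the Step 2 set-up, a random-intercept logistic model tested by likelihood ratio gave 3.3–8.3% with 27, 45 and 72 surgeons. It helps, but is not exact with few surgeons.

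**Step 4: patient characteristics.** A patient-level covariate in the same ordinary model kept 3.2–6.1%.

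**The case against.** The strongest objection is that every figure rests on inputs the documents do not supply, and that milder choices leave little inflation. That stands. Section 8.d points to many surgeons per site, which favours the low end. The background section cites a 43-patient study in which all surgeons found routine use useful; if answers here sit near that ceiling, the problem largely disappears. A reader might infer that the error rate is at least doubled wherever the ICC is 0.20 or more, or wherever there are 45 or fewer surgeons. That is not so: at 95% Yes and ICC 0.20 the rate is 9.4% with 72 surgeons and 7.7% with 90, and at 95% Yes, 45 surgeons and ICC 0.07 it is 6.0%.

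It could also be said that a generalized linear model is loose wording that includes mixed models. This is weak, because the same section names mixed models where it wants them.

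A reader might extend the criticism to the effect-modifier models. The documents do not support calling those wrong: that sentence allows generalized mixed models and leaves the random effects open. It is incomplete, not in error.

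Finally, the analysis is minor: last in 13.b, with no significance level or decision rule. That stands and limits the weight of the point.

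**Conclusion.** The point holds for one test: NIFC-only reported helpfulness against surgeon's experience. The planned model understates the standard error whenever surgeons differ in opinion. The excess in false positives ranges from negligible to several-fold, depending on the number of surgeons, the within-surgeon correlation and the Yes rate, none of which is stated, and on an assumed two-sided 5% level.

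The item 12 confidence question might suggest that the Surgeon Confidence Level endpoint is affected too. That endpoint is listed as a comparison between arms; its association with experience inside the NIFC arm is not listed. Nor does the point reach the teaching-tool objective, which rests on detection rates for students and residents. This is a correction worth making before analysis, not a threat to the trial's main conclusions.

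**What to change.** In 13.b, for the surgeon-experience test of the NIFC-only outcomes, replace the plain logistic or generalized linear model with a logistic model that treats performing surgeon as the cluster. Either of these would do:
- a random intercept for surgeon, with site in the model; or
- GEE or cluster-robust variance.

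Base the degrees of freedom on the number of surgeons, since a random intercept alone reached 8.3% in the check above. Report the number of surgeons and the estimated ICC, and state the significance level. The maneuver is meant for cases where the cystic duct is not seen, so its data may be sparse; if they cannot support this model, report them descriptively.

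The cost is a sentence or two. Surgeon identity and experience are already on the form and R is already the planned software, so no new data or patients are needed. The price is wider intervals for experience effects.

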When responding to an information request that stops the FDA Review Clock (e.g., an AI request or refuse to accept (RTA) decision), you must submit your complete response with valid electronic copy (eCopy) to the Document Control Center (DCC) at the above address. An incomplete response or a response sent any other way (e.g., to another address or via email) will not be considered an official response and will not restart the FDA Review Clock. For more information about FDA's eCopy program, including the new technical standards for an eCopy, refer to the guidance document, "eCopy Program for Medical Device Submissions" at <http://www.fda.gov/downloads/MedicalDevices/DeviceRegulationandGuidance/GuidanceDocuments/UCM313794.pdf>.

Multi-center Study Protocol: Efficacy of Near Infrared Incisionless Fluorescent Cholangiography (NIFC) during Laparoscopic Cholecystectomy

To learn more about the overall 510(k) submission process, please refer to our website at <http://www.fda.gov/MedicalDevices/DeviceRegulationandGuidance/HowtoMarketYourDevice/PremarketSubmissions/PremarketNotification510k/default.htm>.

If you have any procedural or policy questions, please refer to our website at <http://www.fda.gov/MedicalDevices/ResourcesforYou/Industry/default.htm> or contact the Division of Industry and Consumer Education (DICE) at its toll-free number [contact], [contact], or [contact].

Sincerely yours,

[name]
Director, 510(k) Program
Premarket Notification (510(k)) Staff
Office of Device Evaluation
Center for Devices and Radiological Health

c. Pre-Op Case Report Form

Near Infrared Incisionless Fluorescent Cholangiography (NIFC)

PRE-OPERATIVE CASE REPORT FORM

INSTITUTION: _____ PATIENT ID: _____ PROCEDURE DATE: _____

NAME OF PERSON COMPLETING FORM: _____

PATIENT INFORMATION:

Age: _____ Sex: M F Height: _____ Weight: _____ BMI: _____

Known allergy to Iodides? No Yes If yes, **EXCLUDE FROM STUDY!!**

Liver Disease? No Yes If yes, what type? Cirrhosis fatty liver other: _____

LABORATORY TESTS (within 15 days prior to surgery date):

PREGNANCY TEST? Negative Not Done

IMAGING STUDIES:

- LITHIASIS? No Yes If Yes,
Diagnosed by: Ultrasound CT Scan MRCP EUS ERCP

- ERCP/ES? No Yes If Yes,
Date performed: _____ Stones in Bile Duct? No Yes

SPHINCTEROTOMY performed? No Yes

SURGERY STATUS: Elective Urgent Emergency

MULTICENTER TRIAL Page 1 of 1 PREOP-CRF v1.0

d. Intra-Op Case Report Form – Surgeon

Near Infrared Incisionless Fluorescent Cholangiography (NIFC)
INTRA-OPERATIVE CASE REPORT FORM - PERFORMING SURGEON

INSTITUTION: _____ PATIENT ID: _____ PROCEDURE DATE: _____

SURGEON NAME: _____
(PRINT) _____ (SIGNATURE) _____

ACADEMIC TITLE: _____ Years in practice: _____ Approx. #Lap Choles Performed: _____

STUDY ARM: **WLI** (STD mode on light source only) **NIFC** (using both STD and ICG modes)

1. For NIFC group only:

- Time of ICG Administration: _____ AM / PM
- Was there an Adverse Reaction to the ICG? Yes No
If Yes, how was it detected? _____
If Yes, how was it managed? _____

2. PRE-DISSECTION

A. Categorize the initial visualization:

- Amount of fat: Can you see the Cystic Artery? Yes No
- Level of inflammation: Minimal Moderate Significant
- Were adhesions and/or scar tissue needed to be removed prior to visualization? Yes No

B. Remove the fat from the Calot's triangle area, retract the gallbladder and Hartmann's pouch.

C. Document visualization of extra-hepatic biliary anatomy:

For both arms, scope the Calot's triangle area using STD (white-light) mode. If in the NIFC arm, toggle between STD and ICG modes on light source as needed. Check the appropriate boxes below based on what is visible:

Time of Initial Visualization: _____ AM / PM

	Yes	Maybe	No
Cystic Duct			
Right Hepatic Duct			
Common Hepatic Duct			
Common Bile Duct (CBD)			
Cystic-CBD junction			
Cystic-Gallbladder junction			
Accessory Ducts			

D. For NIFC Arm Only: "Reflux Maneuver" Attempted? Yes No
If the Cystic Duct cannot be visualized with fluorescence, use anatraumatic laparoscopic instrument to push on the Common Bile Duct in order to move more of the ICG from the Common Bile Duct through the Cystic Duct into the Gallbladder – thereby increasing visualization of the Cystic Duct - Gallbladder Union. Check the appropriate boxes based on what is visible:

	Yes	Maybe	No
Cystic Duct			
Cystic-CBD junction			
Cystic-Gallbladder junction			

MULTICENTER TRIAL

Page 1 of 2

SURG-CRF v1.0

Multi-center Study Protocol: Efficacy of Near Infrared Incisionless Fluorescent Cholangiography (NIFC) during Laparoscopic Cholecystectomy

Near Infrared Incisionless Fluorescent Cholangiography (NIFC)
INTRA-OPERATIVE CASE REPORT FORM - PERFORMING SURGEON

START DISSECTION: Time of hilar dissection: _____ AM / PM

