We will evaluate the usefulness of the Reflux Maneuver to visualize the Cystic Duct.

8. Design

a. Study Population

Participants will include patients aged 18-years old and above selected for Laparoscopic Cholecystectomy (LC).

b. Setting(s)

Participants will be recruited by the Department of Surgery at the following study sites, all of which are recognized hepato-bilio-pancreatic surgery centers:

- Cleveland Clinic (Weston, FL, USA)

Multi-center Study Protocol: Efficacy of Near Infrared Incisionless Fluorescent Cholangiography (NIFC) during Laparoscopic Cholecystectomy

- Cleveland Clinic (Cleveland, OH, USA)
- Cedars-Sinai Medical Center (Los Angeles, CA, USA)
- Hospital de Clínicas José de San Martín (Buenos Aires, Argentina)
- Tokyo Medical University Hospital (Tokyo, Japan)
- Asklepios Westklinikum (Hamburg, Germany)
- University of Insurbia (Varese, Italy)
- Klinikum Südstadt Rostock (Rostock, Germany)
- Kliniken Essen-Mitte (Essen, Germany)

Surgeons trained in laparoscopic and hepato-bilio-pancreatic (HBP) surgery will participate in the study. Principal and Lead Site Investigators of this Protocol are seniors and recognized HBP surgeons. Additionally, junior surgeons will be involved in the study. When a resident is present in the OR, he/she will perform the procedure under the supervision of the senior surgeon.

c. Enrollment Process

Eligible patients will be identified through clinical and test evaluation. Eligibility will be verified by the patient's primary surgeon. The surgeon will determine the indication and date of the surgery. Once a patient is confirmed as eligible, the surgeon will introduce the study in detail. If after being introduced to the study and having had the opportunity to ask questions, the patient is willing to participate, he/she will be asked to review and sign the informed consent document (Appendix XXX).

Upon entry in the clinical trial patients will be randomly allocated to the intervention arm. Data will be collected at enrolment time, during surgery, at the end of surgery and one week after surgery.

d. Randomization Process

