- Incidence of Anatomic Anomalies of the extra-hepatic biliary system, including any Accessory Ducts
- Incidence of performing IOC
- Incidence of CBD stones
- Incidence of Conversion to open surgery
- Incidence of Bile Duct Injury (BDI)?

iv. For NIFC arm only

- PRIOR to and AFTER DISSECTION: Surgeon/Observer documents which extra-hepatic biliary structures are identified without doubt using the "Reflux Maneuver" during NIFC
- Was the "reflux maneuver" useful?
- Surgeon preference: Was NIFC helpful?

c. One-week Post-Op data collection (usual control after surgery)

- Length of hospital stay

- Readmission?
- Complications?
 - Adverse drug reactions
 - Hemorrhage
 - Bile leak
 - Bile duct injury
- Death?

10. Subject Selection

a. Inclusion Criteria

1. Patients of both genders
2. Minimum age: 18 years old
3. Spoken and written command of the language spoken in the country's center
4. Ability to understand and follow the study procedures and sign the informed consent

b. Exclusion Criteria

1. Known allergies to iodides
2. Known history of cholangitis, pancreatitis, CBDS's, coagulopathy
3. Known liver disease
4. Women who are pregnant or breastfeeding, or for whom possibility of pregnancy was not ruled out

11. Study Device

a. Indocyanine Green (ICG) Fluorescent Dye

The drug used in these studies to evaluate the extra-hepatic bile duct is indocyanine green (ICG) and the equipment uses a wavelength around 800 nm (32,33,34,35,36,37). ICG, a cyanine dye, has been used in various medical diagnostic procedures since its FDA approval in 1956 (38).

ICG is a fluorophore responding to near-infrared irradiation that absorbs light between 790 and 805 nm, and re-emits it with an excitation wavelength of 835 nm. When given intravenously, ICG binds to plasma proteins and becomes confined to the intravascular space [15]. It is then exclusively metabolized by the liver and excreted by the biliary system 15 to 20 minutes after administration. These properties, in conjunction with the absence of any native biological fluorescence within these wavelengths, make ICG an ideal agent for the acquisition of high-quality images of the biliary tract.

b. Equipment

KARL STORZ (Tuttlingen, Germany) has developed a laparoscopic fluorescence imaging system that is suitable for both near-infrared fluorescence and xenon

Multi-center Study Protocol: Efficacy of Near Infrared Incisionless Fluorescent Cholangiography (NIFC) during Laparoscopic Cholecystectomy

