1. PRE-DISSECTION

A. Remove the fat from the Calot's triangle area, retract the gallbladder and Hartmann's pouch.

B. Document visualization of extra-hepatic biliary anatomy:

For both arms, scope the Calot's triangle area using STD (white-light) mode. If in the NIFC arm, toggle between STD and ICG modes on light source as needed. Check the appropriate boxes below based on what is visible:

	Yes	Maybe	No
Cystic Duct			
Right Hepatic Duct			
Common Hepatic Duct			
Common Bile Duct (CBD)			
Cystic-CBD junction			
Cystic-Gallbladder junction			
Accessory Ducts			

C. For NIFC Arm Only: REFLUX MANEUVER

If the Cystic Duct cannot be visualized with fluorescence, use an atraumatic laparoscopic instrument to push on the Common Bile Duct in order to move more of the ICG from the Common Bile Duct through the Cystic Duct into the Gallbladder – thereby increasing visualization of the Cystic Duct - Gallbladder Union. Check the appropriate boxes based on what is visible:

	Yes	Maybe	No
Cystic Duct			
Cystic-CBD junction			
Cystic-Gallbladder junction			

MULTICENTER TRIAL

Page 1 of 2

OBS-CRF v1.0

Multi-center Study Protocol: Efficacy of Near Infrared Incisionless Fluorescent Cholangiography (NIFC) during Laparoscopic Cholecystectomy

Near Infrared Incisionless Fluorescent Cholangiography (NIFC)

INTRA-OPERATIVE CASE REPORT FORM - OBSERVER

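### The intra-operative forms do not record the cystic duct in ICG mode before or after the Reflux Maneuver, and they omit the planned usefulness question, so its usefulness is only partly derivable

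*Combined protocol and SAP*

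**What the plan says.** Section 7.a (Additional Observations, NIFC group only) describes the maneuver as an option when the cystic duct is not seen with NIFC because it may hold no ICG. It then commits to an evaluation: "We will evaluate the usefulness of the Reflux Maneuver to visualize the Cystic Duct".

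- **Trigger before dissection.** Surgeon form item 2.D and observer form item 1.C both start from "If the Cystic Duct cannot be visualized with fluorescence".
- **Reading before the maneuver.** Surgeon item 2.C and observer item 1.B each have a single Yes/Maybe/No grid, completed under the instruction "If in the NIFC arm, toggle between STD and ICG modes on light source as needed". There is no box for the mode in which a structure was seen. The after-dissection grids (surgeon 3.A, observer 2.A) work the same way.
- **Reading after the maneuver.** A second grid covers the cystic duct and the two junctions. It asks what is visible and names no mode.
- **After dissection.** Items 3.B and 2.B say only "Repeat the Reflux Maneuver. Check the appropriate boxes based on what is visible", with no trigger restated.
- **Attempt field.** The surgeon form has a Yes/No box for whether the maneuver was attempted. The observer item, headed "C. For NIFC Arm Only: REFLUX MANEUVER", has none, and neither does the observer's after-dissection item.
- **Direct question.** Section 9.b.iv lists "Was the 'reflux maneuver' useful" for the NIFC arm, and section 13.b plans to model the reported helpfulness of the maneuver. Surgeon item 12 asks only about safety, confidence and preference for NIFC. The observer form has no feedback item.

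**The concern.** The maneuver works by moving dye, so the state it is meant to change is the visibility of the cystic duct in ICG mode. No form item records that state. A duct seen only in white light is marked Yes before the maneuver. If fluorescence then appears, the record runs from Yes to Yes and the success cannot be seen. If fluorescence does not appear, the duct is still visible in white light, so the later Yes can be counted as a success that did not happen.

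The subjective route is also broken, because the question that would supply the outcome for the section 13.b model is on neither form.

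At stake is a stated evaluation in the NIFC arm. The reported usefulness of the maneuver could depend on how the boxes are summarised rather than on what the maneuver did.

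**Working it through.** The plan gives no figure for the maneuver, so there is none to reproduce. The check traces what the boxes can show and then illustrates the size.

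**Inputs from the documents**
- NIFC arm: 500 patients (section 13.a).
- White-light cystic duct detection assumed for the control arm: 50% before dissection, 100% after (table in section 13.a).
- Junctions after dissection, control arm: Cystic-CBD 60%, Cystic-Gallbladder 70% (same table).
- Fluorescence rates in section 2.b: cystic duct 93% before dissection in one series, 95.1% after complete dissection in another, and all 52 patients in a third. A general range of 71 to 100% is given for the extra-hepatic bile duct, not for the cystic duct.

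**Assumed, not in the documents**
- w: share of triggered patients whose duct is visible in white light, varied from 0 to 0.75.
- s: true share in whom the maneuver brings the duct into view in ICG mode, set at 50% and taken as unrelated to w.
- Maybe counts as not Yes, in line with the without-doubt standard in section 9.b.

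**Step 1: how many patients before dissection.** With f the share not seen by fluorescence, triggered = 500 × f. Of these, 500 × f × w already read Yes and can show no change, and 500 × f × (1 − w) remain readable. With w = 0.5:
- f = 0 (52 of 52 seen): no patients triggered.
- f = 1 − 0.951 = 0.049: 24.5 triggered, 12.25 readable.
- f = 1 − 0.93 = 0.07: 35 triggered, 17.5 readable.
- f = 1 − 0.71 = 0.29: 145 triggered, 72.5 readable. This is an outer bound, because the 71% is not a cystic duct figure.

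**Step 2: what the same data can be made to say.** Three summaries are possible:
- A, Yes on the maneuver grid in any mode, over all attempted: w + (1 − w)s.
- B, moved from not-Yes to Yes, over all attempted: (1 − w)s.
- C, moved to Yes, among those not-Yes beforehand: s.

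| w | A | B | C |
|---|---|---|---|
| 0 | 50% | 50% | 50% |
| 0.25 | 62.5% | 37.5% | 50% |
| 0.5 | 75% | 25% | 50% |
| 0.75 | 87.5% | 12.5% | 50% |

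For w = 0.5: A = 0.5 + 0.5 × 0.5 = 0.75, and B = 0.5 × 0.5 = 0.25. A overstates, B understates, and C is right only if success is unrelated to white-light visibility.

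**Step 3: after dissection.** If the 100% planning value carries over to triggered NIFC patients, w = 1. Then A = 100%, B = 0, and C has no patients. For the junctions, the control values leave 100 − 60 = 40% and 100 − 70 = 30% not seen in white light, so a gain there can still appear. The reading in 3.A may also follow an earlier maneuver that has already moved dye.

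**The case against.** A reader might infer that usefulness cannot be derived at all, or that the forms guarantee an understated or zero result. The documents do not support either reading.

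- **The readable subset.** Patients marked No or Maybe in 2.C were not clearly seen in either mode, so a move to Yes in 2.D is a genuine before/after change. This stands. The subset leaves out everyone whose duct was visible in white light, and the maneuver grid still names no mode.
- **The attempt box as proxy.** On the surgeon form before dissection, an attempt implies fluorescence failure if the trigger was followed. Section 9.b.iv describes the maneuver reading as made during NIFC, so a success share could be computed. This stands only under both assumptions. Section 7.a leaves the maneuver optional, the observer form has no such box, and section 12.c.ii describes NIFC itself as toggling between the two modes.
- **Direction of bias.** The plan specifies no before/after change score, and one natural summary overstates success. This stands: the direction is open.
- **After dissection.** The 100% is a control-arm planning value for one structure, not a result, and the maneuver grid also covers both junctions. This stands.
- **Size.** Independence of white-light and fluorescence visibility is unsupported, and in one cited series almost nobody would meet the trigger. This stands, so the counts are illustrations.
- **Video.** Surgery is recorded from the first view of Calot's triangle, but no mode-specific reading of the recording is planned.
- **Importance.** The maneuver is neither a primary nor a secondary endpoint and involves no comparison between arms. This stands and limits the priority.

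**Conclusion.** The concern holds in a limited form. The trigger is specific to fluorescence, the reading before the maneuver is not, the reading after it has no stated mode, and the planned usefulness question is missing from both forms. These facts come from the forms and need no assumption.

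Usefulness for the cystic duct is cleanly readable only in the pre-dissection subset not clearly seen in either mode. For all attempted patients it requires assuming that the trigger was followed and that the maneuver grid was read in ICG mode. Without that, a true 50% can read as 25% or 75% at w = 0.5, and as 12.5% or 87.5% at w = 0.75. Those figures rest on an assumed w and s, and on success being unrelated to white-light visibility.

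After dissection, little or no cystic duct gain can be read if the 100% planning value holds; the junctions keep headroom. The priority is low.

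**What to change.** The changes apply to the NIFC arm and affect recording and analysis only:

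1. Directly before surgeon items 2.D and 3.B and observer items 1.C and 2.B, add a row: *In ICG mode, before the maneuver: Cystic Duct, Cystic-CBD junction, Cystic-Gallbladder junction (Yes / Maybe / No)*.
2. State on both forms that the maneuver boxes are read in ICG mode.
3. Add the Yes/No attempt box to the observer form, before and after dissection.
4. Add the section 9.b.iv usefulness question to the forms, so that the model in section 13.b has its outcome.
5. In section 7.a or 13.b, define usefulness as the share of attempted patients who move from not-Yes to Yes in ICG mode before dissection. Report separately the number attempted whose ICG-mode reading was already Yes. Treat the after-dissection repeat as descriptive.

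The conditional wording before dissection and the unconditional wording of items 3.B and 2.B should also be reconciled.

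The cost is a few more tick boxes and seconds per NIFC case, plus a sentence or two in the protocol. Rows 1 to 4 have to be in place before the surgery concerned, because without a planned mode-specific video reading the missing state cannot be recovered later.
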